6.3 SAFETY ANALYSIS

Incidence and severity of AEs will be described for all treated patients by treatment group as received and by the Medical Dictionary for Regulatory Activities (MedDRA) classification.

Safety outcomes include incidence of sICH within 36 hours (primary safety assessment), any ICH within 36 hours, overall mortality, and stroke-related and neurological deaths within 90 days of study drug initiation. The cumulative incidences of each outcome will be compared via Fisher's exact test. Mortality will be analyzed by Log-Rank test and the Kaplan-Meier estimates will be plotted over the observation period of 90 days. No alpha adjustment for multiple testing on the safety endpoints is foreseen because those analyses will be exploratory.

6.4 EXPLORATORY ANALYSES

As exploratory analyses, heterogeneity of treatment effect of alteplase will be evaluated by various pre-specified baseline covariates. The primary pre-specified variables and their analytic thresholds are defined by:

- Age (<65 vs. ≥65)
- Pre-treatment NIHSS score (0–2 vs. 3–5)
- Last known well time to treatment (0–2 vs. >2–3 hours)
- Stroke subgroup (RISS vs. non-RISS)

Additional heterogeneity analyses will be considered and detailed in the SAP. Forest plots will be constructed to illustrate subgroup analyses. In addition, the two-way interactions of IV alteplase treatment effect with age, NIHSS score, and stroke subgroups (RISS vs. non-RISS) on the primary outcome will be explored through multivariable logistic regression. Additional exploratory analyses will be conducted to explore treatment effects on quality of life endpoints and other exploratory endpoints.

6.5 INTERIM ANALYSIS

One interim analysis of the primary efficacy outcome is planned for clear futility, conducted according to the beta-spending approach ([Pampallona et al. 2001](#)) with an O'Brien-Fleming-type boundary. This futility analysis will occur after approximately 50% of patients (or 474) have completed the 90-day assessment.

An independent Data Coordinating Center (iDCC) will be responsible for the preparation and review of unmasked data.

Alteplase—Genentech, Inc.
59/Protocol ML29093, Version 3

An iDMC will be organized for review of the interim analysis results. The composition of the iDMC and analysis in detail will be documented in a separate iDMC charter.

6.6 MISSING DATA HANDLING

Under the ITT principle, all patients who are randomized will be included in the analysis. The multiple-imputation method will be used for handling missing data, including the last observation (e.g., the Day 30 mRS) among the variables used in imputation. As supportive analyses, missing primary outcome data will be imputed by 1) using last observation carried forward and 2) assuming missing outcomes to be unfavorable.

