4.6.4 Visit 4 (Day 30 [30 ± 7 Days])

A phone call to the patient or caregiver will be made at Day 30 and an mRS will be assessed (see [Appendix 8](#)). AEs, concomitant medications, and patient survival will be assessed during this phone visit. Pregnancy will also be assessed for female patients of childbearing potential.

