6.1 DETERMINATION OF SAMPLE SIZE

A sample size of 856 is required in order to achieve 80% power in the primary analysis to detect an effect size of 9% absolute difference in the proportion of patients with favorable outcomes between the alteplase and control arms. The above sample size calculation assumes a control proportion of 65% and Type I error probability of 0.025 (one-sided), and uses a group sequential design with one interim analysis for futility (non-binding), based on an O'Brien-Fleming boundary, after 50% of the anticipated sample size have completed the 90-day follow-up assessments. [REDACTED] was used for this sample size calculation.

The ITT principle will be applied to the primary analysis and, therefore, to safeguard against dilution of the treatment effect associated with an approximate 5% non-adherence rate (due to lost to follow-up, consent withdrawal, treatment crossovers, and stroke mimics), the above sample size needs to be inflated by a factor of 1/0.95² or 1.108 ([Friedman et al. 1998](#)). Therefore, a total sample size of 948 is required for this study.

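### The two supportive missing-data analyses apply one rule to both arms, so with similar dropout in each arm they can miss the fragility of a borderline result

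*Protocol*

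**What the plan says.** Protocol Version 3, Section 6.6, keeps all randomized patients in the analysis and makes multiple imputation the main method, with the Day 30 mRS as one of the predictors in the imputation model. Two simpler rules are then listed as support: "missing primary outcome data will be imputed by 1) using last observation carried forward and 2) assuming missing outcomes to be unfavorable". Neither rule lets the assumption about missing patients differ by arm. The section attaches no decision rule to these analyses and, unlike Sections 6.2 and 6.4, does not defer detail to the SAP.

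The only mRS scheduled between treatment and Day 90 is in Section 4.6.4: "A phone call to the patient or caregiver will be made at Day 30 and an mRS will be assessed". The early-discontinuation contact (Section 4.6.6 and Appendix 1) collects medications, adverse events and survival, but no mRS.

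Section 6.1 allows for an "approximate 5% non-adherence rate". This pools loss to follow-up, consent withdrawal, treatment crossovers and stroke mimics. No rate is given for missing Day 90 outcomes alone.

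**The concern.** Multiple imputation here assumes that, given the Day 30 mRS and the other model variables, missing patients resemble observed ones. A supportive analysis is useful if it shows how far that assumption can fail before the conclusion changes. The departure that would bias a treatment comparison is one that differs by arm.

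LOCF reuses a value the imputation already conditions on, adds the cruder assumption of no change after Day 30, and has no stated rule for patients lost before Day 30. Missing = unfavorable treats both arms alike, so with balanced dropout it shrinks the difference slightly and does little else.

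Loss that differs by arm is conceivable. The protocol assumes 2% v 0% symptomatic hemorrhage (Section 1.3), permits unblinding for hemorrhage or worsening (Section 4.2), and ends follow-up when consent is withdrawn (Section 4.7.1). Nothing shows that it will occur. At stake is how a narrowly significant result is read. The primary test and the sample size are not affected.

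**Working it through.** **The plan's own figures.** Inputs from Section 6.1: 65% v 74%, one-sided 0.025, 80% power, and one non-binding O'Brien-Fleming-type futility look at 50%.
- Fixed design, unpooled: 2 × (1.960 + 0.842)² × (0.65×0.35 + 0.74×0.26) / 0.09² = 814 in total.
- The futility look (Lan-DeMets form assumed) inflates this by 1.052, giving 856. Then 856 / 0.95² = 948, or 474 per arm. Both figures reproduce.

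**Significance threshold.** 1.96 × √(2 × 0.695 × 0.305 / 474) = 5.86 points. All tests here are unstratified approximations to the stratified primary test.

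**Balanced dropout, m = 5% per arm (assumed).** Under missing = unfavorable the difference is (1 − m)(pT − pC).
- 74% v 65%: 0.95 × 9.0 = 8.55 points, z 2.78.
- 72% v 65%: 0.95 × 7.0 = 6.65 points, z 2.15, still significant.
- 72% v 65%, with missing alteplase patients at 42% (30 points below MAR): 0.95×72 + 0.05×42 − 65 = 5.5 points, z 1.81, not significant.

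**LOCF, 24 of 474 missing per arm, observed difference 9.0.** Assumed Day 30 rates of 50–74% (alteplase) and 60–65% (control) give 8.0 to 9.1 points, p = 0.003 to 0.008.

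**Tipping point with imputation variance.** For each arm with n observed, M missing, observed rate p, imputed rate r and overall rate q, the variance is q(1−q)/474 + (M/474)²[r(1−r)/M + p(1−p)/n]. Control is 65%. The last column is the shift below MAR, in missing alteplase patients only, at which p reaches 0.05.

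| Observed difference | Missing per arm | Imputation p | Missing = unfavorable p | One-arm shift that tips |
|---|---|---|---|---|
| 9.0 | 14 (3%) | 0.003 | 0.004 | none |
| 9.0 | 24 (5%) | 0.003 | 0.006 | 58 points |
| 9.0 | 47 (10%) | 0.004 | 0.010 | 28 points |
| 7.0 | 14 (3%) | 0.022 | 0.027 | 33 points |
| 7.0 | 24 (5%) | 0.023 | 0.032 | 18 points |
| 7.0 | 47 (10%) | 0.027 | 0.046 | 8 points |
| 6.5 | 14 (3%) | 0.034 | 0.040 | 16 points |
| 6.5 | 24 (5%) | 0.036 | 0.047 | 8 points |
| 6.5 | 47 (10%) | 0.041 | 0.064 | 3 points |

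In every row but the last, missing = unfavorable stays below 0.05.

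**Unbalanced dropout, observed 74% v 65%.**
- 33 alteplase v 14 control missing (7% v 3%): 0.74×441/474 − 0.65×460/474 = 5.8 points, p = 0.061, while the imputation result stays at 9.0 (p = 0.003).
- Reversed (3% v 7%): 0.74×460/474 − 0.65×441/474 = 11.3 points, p = 0.0002.

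**How often a result is borderline.** With a true 9-point difference, the standard error is √((0.2275 + 0.1924)/474) = 2.98 points. The chance of exceeding 5.86 points is about 0.854, and of exceeding 7.0 about 0.749. So (0.854 − 0.749)/0.854, about 12% of significant results, fall below 7 points. A smaller true effect raises that share.

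**The case against.** The strongest reply is that nothing in Section 6.6 is wrong. It names a principled main method and two conventional checks, and further sensitivity analyses usually belong in the SAP, which was not available for this review. That limits the weight of the point but does not remove it: the section itself chooses LOCF as one of its two checks, and LOCF is a weak choice when its only source is already in the imputation model.

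A reader might infer more than the documents support, in three ways.
- *That the two checks can hardly alter the result.* This is true only for balanced dropout. If alteplase patients were lost because they did worse, more of them would probably be missing, and missing = unfavorable reacts strongly to that (9.0 to 5.8 points at 7% v 3%).
- *That arm-specific loss is never examined.* Imputation and LOCF both use each patient's own Day 30 score, so arm differences visible by then do enter. What goes untested is a departure that differs by arm after Day 30, or among patients lost before it.
- *That the trial would declare its finding robust on these checks.* Section 6.6 makes no such claim.

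The 5% is also borrowed. Crossovers and mimics need not have missing outcomes. Telephone mRS at Day 90 is allowed (Appendix 1), and patients with anticipated loss to follow-up are excluded (Section 4.1.2). These points stand.

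**Conclusion.** The point holds in a limited form, as a cheap improvement. The stated supportive analyses do not vary the missing-data assumption by arm. With similar dropout in both arms they can leave a result of about 6.5 to 7 points looking secure when, at 5% missing per arm, an 8- to 18-point shift in the missing alteplase patients would remove significance.

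It does not extend to the design effect. At 9 points and 5% missing per arm, missing alteplase patients would have to respond 58 points below MAR (about 16% instead of 74%), which is not plausible. At 3% missing, no alteplase-only shift suffices. The extreme case of every missing alteplase patient failing and every missing control succeeding gives 0.95×74 − (0.95×65 + 5) = 3.55 points (z 1.18), but that is a bound and not a scenario to expect.

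The missing rates, Day 30 rates and shifts are all assumptions, since the protocol supplies none.

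**What to change.** In Section 6.6, replace the LOCF analysis with a two-way delta-adjusted tipping-point analysis on the same multiple imputation. Vary the probability of a favorable outcome among missing patients separately in each arm, and report the combinations at which the primary conclusion changes. Keep missing = unfavorable as one point on that grid. Report the number missing by arm alongside, because the behavior of that single point depends on whether dropout is balanced.

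The cost is one sentence in the protocol and modest programming on an imputation that is already planned. The downside is a table of results instead of one p-value. The primary analysis and the sample size do not change.

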7. DATA COLLECTION AND MANAGEMENT

7.1 DATA QUALITY ASSURANCE

The Sponsor will supply eCRF specifications for this study. A contract research organization (CRO) will be responsible for data management of this study, including quality checking of the data. Data entered manually will be collected via EDC using eCRFs. Sites will be responsible for data entry into the EDC system. In the event of discrepant data, the CRO will request data clarification from the sites, which the sites will resolve electronically in the EDC system.

The CRO will produce a Data Quality Plan that describes the quality checking to be performed on the data with the input from the Sponsor. For this study, local laboratories will be used and data will be captured in the EDC system and will then be transferred to the Sponsor. This will include the eCRF data using the Sponsor's standard procedures and processes to transfer data.

The Sponsor will perform oversight of the data management of this study, including approval of the CRO's data management plans and specifications. Data will be transferred electronically from the CRO to the Sponsor, and the Sponsor's standard procedures will be used to handle and process the electronic transfer of these data.

eCRFs and correction documentation will be maintained in the EDC system's audit trail. The EDC vendor has back-ups for data stored, and records retention for the study data will be consistent with the CRO's standard procedures.

Data from paper PRO questionnaires will be entered into the EDC system by site staff.

7.2 ELECTRONIC CASE REPORT FORMS

eCRFs are to be completed using a Sponsor-designated EDC system. Sites will receive training and have eCRF completion guidelines for the eCRF completion. eCRFs will be submitted electronically to the Sponsor and should be handled in accordance with instructions from the Sponsor.

Alteplase—Genentech, Inc.
60/Protocol ML29093, Version 3

All eCRFs should be completed by designated trained site staff. eCRFs should be reviewed and electronically signed and dated by the investigator or a designee.

At the end of the study, the investigator will receive patient data for his or her site in a readable format on a compact disc that must be kept with the study records.

Acknowledgement of receipt of the compact disc is required.

7.3 SOURCE DATA DOCUMENTATION

Study monitors will perform ongoing source data verification to confirm that critical protocol data (e.g., source data) entered into the eCRFs by authorized site personnel are accurate, complete, and verifiable from source documents. Source documents (paper or electronic) are those in which patient data are recorded and documented for the first time. They include, but are not limited to, hospital records, clinical and office charts, laboratory notes, memoranda, patient-reported outcomes, evaluation checklists, pharmacy dispensing records, recorded data from automated instruments, copies of transcriptions that are certified after verification as being accurate and complete, microfiche, photographic negatives, microfilm or magnetic media, X-rays, patient files, and records kept at pharmacies, laboratories, and medico-technical departments involved in a clinical trial.

Before study initiation, the types of source documents that are to be generated will be clearly defined in the Study Trial Monitoring Plan. This includes any protocol data to be entered directly into the eCRFs (i.e., no prior written or electronic record of the data) and considered source data.

Source documents that are required to verify the validity and completeness of data entered into the eCRFs must not be obliterated or destroyed and must be retained per the policy for retention of records described in Section [7.5](#).

To facilitate source data verification, the investigators and institutions must provide the Sponsor direct access to applicable source documents and reports for trial-related monitoring, Sponsor audits, and IRB/EC review. The investigational site must also allow inspection by applicable health authorities.

7.4 USE OF COMPUTERIZED SYSTEMS

When clinical observations are entered directly into an investigational site's computerized medical record system (i.e., in lieu of original hardcopy records), the electronic record can serve as the source document if the system has been validated in accordance with health authority requirements pertaining to computerized systems used in clinical research. An acceptable computerized data collection system allows preservation of the original entry of data. If original data are modified, the system should maintain a viewable audit trail that shows the original data as well as the reason for the change, name of the person making the change, and date of the change.

Alteplase—Genentech, Inc.
61/Protocol ML29093, Version 3

7.5 RETENTION OF RECORDS

Records and documents pertaining to the conduct of this study and the distribution of IMP, including eCRFs, PRO data (if applicable), Informed Consent Forms, laboratory test results, and medication inventory records, must be retained by the Principal Investigator for at least 15 years after completion or discontinuation of the study, or for the length of time required by relevant national or local health authorities, whichever is longer. After that period of time, the documents may be destroyed, subject to local regulations.

No records may be disposed of without the written approval of the Sponsor. Written notification should be provided to the Sponsor prior to transferring any records to another party or moving them to another location.

8. ETHICAL CONSIDERATIONS

8.1 COMPLIANCE WITH LAWS AND REGULATIONS

This study will be conducted in full conformance with the International Conference on Harmonisation E6 guideline for Good Clinical Practice and the principles of the Declaration of Helsinki, or the laws and regulations of the country in which the research is conducted, whichever affords the greater protection to the individual. The study will comply with the requirements of the International Conference on Harmonisation E2A guideline (Clinical Safety Data Management: Definitions and Standards for Expedited Reporting). Studies conducted in the United States or under a U.S. Investigational New Drug (IND) application will comply with FDA regulations and applicable local, state, and federal laws. Studies conducted in the European Union (EU)/European Economic Area (EEA) will comply with the EU Clinical Trial Directive (2001/20/EC).

8.2 INFORMED CONSENT

The Sponsor's sample Informed Consent Form (and ancillary sample Informed Consent Forms such as a Child's *Informed Assent Form* or *Home Nursing* Informed Consent Form, if applicable) will be provided to each site. If applicable, it will be provided in a certified translation of the local language. The Sponsor or its designee must review and approve any proposed deviations from the Sponsor's sample Informed Consent Forms or any alternate consent forms proposed by the site (collectively, the "Consent Forms") before IRB/EC submission. The final IRB/EC-approved Consent Forms must be provided to the Sponsor for health authority submission purposes according to local requirements.

The Consent Forms should be revised whenever there are changes to study procedures or when new information becomes available that may affect the willingness of the patient to participate. The final revised IRB/EC-approved Consent Forms must be provided to the Sponsor for health authority submission purposes.

Alteplase—Genentech, Inc.
62/Protocol ML29093, Version 3

Patients must be re-consented to the most current version of the Consent Forms (or to a significant new information/findings addendum in accordance with applicable laws and IRB/EC policy) during their participation in the study. For any updated or revised Consent Forms, the case history or clinical records for each patient shall document the informed consent process and that written informed consent was obtained using the updated/revised Consent Forms for continued participation in the study.

A copy of each signed Consent Form must be provided to the patient or the patient's legally authorized representative. All signed and dated Consent Forms must remain in each patient's study file or in the site file and must be available for verification by study monitors at any time.

For sites in the U.S., each Consent Form may also include patient authorization to allow use and disclosure of personal health information in compliance with the U.S. Health Insurance Portability and Accountability Act of 1996 (HIPAA). If the site utilizes a separate Authorization Form for patient authorization for use and disclosure of personal health information under the HIPAA regulations, the review, approval, and other processes outlined above apply except that IRB review and approval may not be required per study site policies.

8.3 INSTITUTIONAL REVIEW BOARD OR ETHICS COMMITTEE

This protocol, the Informed Consent Forms, any information to be given to the patient, and relevant supporting information must be submitted to the IRB/EC by the Principal Investigator and reviewed and approved by the IRB/EC before the study is initiated. In addition, any patient recruitment materials must be approved by the IRB/EC.

The Principal Investigator is responsible for providing written summaries of the status of the study to the IRB/EC annually or more frequently in accordance with the requirements, policies, and procedures established by the IRB/EC. Investigators are also responsible for promptly informing the IRB/EC of any protocol amendments (Section 9.6).

In addition to the requirements for reporting all AEs to the Sponsor, investigators must comply with requirements for reporting SAEs to the local health authority and IRB/EC. Investigators may receive written IND safety reports or other safety-related communications from the Sponsor. Investigators are responsible for ensuring that such reports are reviewed and processed in accordance with health authority requirements and the policies and procedures established by their IRB/EC, and archived in the site's study file.

8.4 CONFIDENTIALITY

The Sponsor maintains confidentiality standards by coding each patient enrolled in the study through assignment of a unique patient ID number. This means that patient names are not included in data sets that are transmitted to any Sponsor location.

Alteplase—Genentech, Inc.
63/Protocol ML29093, Version 3

Patient medical information obtained by this study is confidential and may only be disclosed to third parties as permitted by the Informed Consent Form (or separate authorization for use and disclosure of personal health information) signed by the patient, unless permitted or required by law.

Medical information may be given to a patient's personal physician or other appropriate medical personnel responsible for the patient's welfare, for treatment purposes.

Data generated by this study must be available for inspection upon request by representatives of the FDA and other national and local health authorities, Sponsor monitors, representatives, and collaborators, and the IRB/EC for each study site, as appropriate.

8.5 FINANCIAL DISCLOSURE

Investigators will provide the Sponsor with sufficient, accurate financial information in accordance with local regulations to allow the Sponsor to submit complete and accurate financial certification or disclosure statements to the appropriate health authorities. Investigators are responsible for providing information on financial interests during the course of the study and for 1 year after completion of the study (i.e., LPLV).

